#### **3.2 STATISTICAL ANALYSES**

##### **3.2.1 STATISTICAL HYPOTHESES**

There is no statistical testing in this study.

##### **3.2.2 GENERAL APPROACH**

All available data will be displayed via subject data listings, and summarized for each evaluation time point as appropriate by study domain (including domain-pooled) and study arm. The categorical data will be summarized with the number of subjects and percentage. Continuous data will be summarized by descriptive statistics (i.e., number of subjects, mean, standard deviation, minimum, maximum, and median).

In general, categorical data will be analyzed by using Fisher's exact test or Cochran-Mantel-Haenszel test stratified by domain for comparing overall treatment group difference. For by-domain subgroup analysis, categorical data will be tested by using Fisher's exact test or Chi-square test.

Continuous data will be analyzed by using analysis of variance (ANOVA) on baseline data, and by using analysis of covariance (ANCOVA) on change data for comparing overall

treatment group difference. Non-parametric method shall be adapted or log-transformation may be needed for non-normally distributed data. For by-domain subgroup analysis, baseline continuous data will be tested by using two-sample t test or Wilcoxon Rank-sum test, post-treatment continuous data will be tested by using ANCOVA or Wilcoxon Rank-sum test.

For the ANOVA and ANCOVA model, factors of treatment, domain (as appropriate), site and baseline value (for post-baseline data) and other baseline factors will be included in the model if significant, those non-statistically significant factors except treatment will be removed from the model (alpha=0.1 for interaction, 0.05 for others).

All statistical tests will be two-sided and evaluated at the 0.05 level of significance. All confidence intervals, if provided, will be the 95% CI.

The most recent value before first dose administration will be defined as the baseline value; therefore, the baseline value will be the outcome of the closest evaluation performed before or equal to the first dosing date.

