## **2.2 RANDOMIZATION AND BLINDING**

The study treatment will be randomly assigned to subjects. The randomized sequence of study treatments will be generated by a qualified biostatistician. The randomization schedule will be kept and maintained by the designated personnel before the study begins and until the database lock. The biostatistician prepares the schedule with a 1:1 randomization ratio (CX-4945: Placebo) by stratified randomization with study domains and study sites strata. Also, block permutation is used for generating randomization schedule.

This is a double-blind study. Neither the subject nor the investigators, clinic administrators, or sponsor staff who involve in the treatment or clinical evaluation of the subjects will be aware of the treatment received either at the time of randomization or later, throughout the conduct of the trial. Assigned unblinded team may include study site staff, CRO's personnel and/or Senhwa Biosciences, Inc's personnel. Other personnels involved in the study (the investigator and the clinical monitor) will be blinded until the database lock.

The treatment codes will not be prematurely broken unless an emergency situation, when the appropriate management of the subject necessitated acknowledgement of the treatment allocation, occurred. In the event of a medical emergency, if possible, the medical monitor should be contacted first to discuss the need for unblinding. For unblinding a subject, the treatment code blind can be obtained by the investigator, by accessing the EDC system.

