## **3.3 STATISTICAL/ANALYTICAL ISSUES**

### **3.3.1 ADJUSTMENTS FOR COVARIATES**

Due to early termination of the study, there was a small number of subjects enrolled at most sites. In addition, there was no similar site-related properties among sites. Therefore, Site is not considered as a factor in the ANOVA and ANCOVA model; only treatment, domain (as appropriate), and baseline value (for post-baseline data) are the factors in the ANOVA and ANCOVA model.

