#### **3.4.3 BY-DOMAIN SUBGROUP ANALYSIS - CONTINUOUS DATA**

For by-domain subgroup analysis, baseline continuous data will be tested by using two-sample t test or Wilcoxon Rank-sum test, post-treatment continuous data will be tested by using ANCOVA or Wilcoxon Rank-sum test.

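### The by-domain rank test for post-treatment continuous data has no baseline covariate, and the pooled rank method is not named

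*SAP*

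**What the plan says.** **Within a domain.** SAP 3.4.3 covers baseline data first: "For by-domain subgroup analysis, baseline continuous data will be tested by using two-sample t test or Wilcoxon Rank-sum test". For later data, "post-treatment continuous data will be tested by using ANCOVA or Wilcoxon Rank-sum test" (also in SAP 3.2.2). Neither section says when to choose which test, or whether ranks are taken on the post-treatment value or on the change. Protocol 7.3 had a t test or rank-sum test for by-domain efficacy data. The SAP raised the parametric option to ANCOVA and left the rank option as it was.

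**Pooled over domains.** SAP 3.2.2 specifies ANCOVA on change and adds: "Non-parametric method shall be adapted or log-transformation may be needed for non-normally distributed data". No pooled rank test, stratum or covariate is named.

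**Adjustment elsewhere.** SAP 3.3.1 says that "only treatment, domain (as appropriate), and baseline value (for post-baseline data) are the factors in the ANOVA and ANCOVA model". SAP 2.2 describes "stratified randomization with study domains and study sites strata". The Cochran-Mantel-Haenszel option for categorical data (SAP 3.2.2) and the log-rank test for fever (SAP 3.2.4) are both stratified by domain.

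**Testing.** "All statistical tests will be two-sided and evaluated at the 0.05 level of significance" (SAP 3.2.2). SAP 3.2.1 says that the study has no statistical testing, but the tests in 3.2.2 will still produce p-values.

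**The concern.** A plain rank-sum test has no place for a covariate. When a by-domain endpoint moves from ANCOVA to ranks, the baseline covariate goes. Ranking the change uses baseline only by subtracting it in full, which is inefficient unless baseline and outcome are strongly correlated. Ranking the post-treatment value ignores baseline altogether. Either way, skewed endpoints would be tested less efficiently than they could be, in domains that may hold only about 11 subjects per arm.

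The pooled analysis raises a different issue. Domain is a randomization stratum, and the plan offers a domain term or a domain-stratified test for the other data types. For ranks it is silent. An analyst might reach for the one rank test that the SAP names. Used unstratified, that test counts the difference between domains as noise while the design has balanced it out, so it becomes conservative. In either setting the risk is that a real effect is reported as null.

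**Working it through.** **The plan's own figure.** There is no power figure for any continuous endpoint. The only sample-size figure is 120 evaluable and about 136 enrolled at 10% attrition. It reproduces as 4 × 34 = 136 if each arm and domain has 30, since 30/0.9 = 33.3, rounded up to 34. Nothing below rests on it.

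**Inputs from the documents.** 44 randomized (SAP 3.4.1); 1:1 within domain (SAP 2.1); two-sided 0.05 (SAP 3.2.2); ANCOVA factors (SAP 3.3.1).

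**Assumptions, not in the documents.** 44/4 = 11 per arm per domain; treatment effect 0.8 SD; baseline-outcome correlation ρ = 0.3, 0.5 or 0.7; domain shift of 0, 0.5, 1 or 2 SD in the post-treatment value. In the log-normal runs the SD is 1 on the log scale, and effects and shifts are on that scale.

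**Mechanism.** With equal unit variances, the variance of a change is 2(1 − ρ) and the residual variance after baseline adjustment is 1 − ρ². Their ratio is (1 − ρ²)/[2(1 − ρ)] = (1 + ρ)/2, which is 0.65, 0.75 and 0.85 at ρ = 0.3, 0.5 and 0.7. Analysing change therefore wastes most at low correlation.

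**By-domain power, 11 per arm.** Log-normal data, 4,000 runs per cell, standard error at most √(0.25/4000) = 0.8 points:

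| Test | ρ = 0.3 | ρ = 0.5 | ρ = 0.7 |
|---|---|---|---|
| Rank-sum on change | 31% | 40% | 59% |
| Rank-sum on post value | 40% | 40% | 41% |
| ANCOVA, raw change | 28% | 31% | 44% |
| Rank ANCOVA (post value on baseline rank) | 42% | 49% | 63% |
| ANCOVA, log scale | 43% | 52% | 68% |

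Rank ANCOVA minus rank-sum on change: 42 − 31 = 11, 49 − 40 = 9 and 63 − 59 = 4 points.

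A separate simulation with the same group size and effect gave these results:
- Log-normal data: rank-sum on change 32/40/59%, rank ANCOVA 43/47/60%. Differences 11, 7 and 1.
- Heavy-tailed t data with 3 degrees of freedom: 46/59/79% against 64/70/80%. Differences 18, 11 and 1.

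The loss is thus 7 to 18 points at ρ = 0.3 to 0.5 and 1 to 4 points at ρ = 0.7. If post-treatment values were ranked instead, the first table gives losses of 42 − 40 = 2, 49 − 40 = 9 and 63 − 41 = 22 points.

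Type I error by domain is nominal: 4.4 to 5.0% for rank-sum on change, 5.1 to 5.2% for rank ANCOVA.

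**Pooled, 44 subjects, log-normal data.** Type I error of an unstratified rank-sum on change, range over the three correlations:
- no domain shift: 4.6 to 4.8%
- 0.5 SD: 3.1 to 4.8%
- 1 SD: 1.7 to 3.4%
- 2 SD: 0.1 to 0.6%

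The van Elteren test stays at 3.8 to 5.1% throughout. Heavy-tailed data with shifts of 1 to 1.5 SD gave 1 to 3% for the unstratified test.

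Pooled results at a 1 SD shift, ρ = 0.3/0.5/0.7:

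| Test | Type I error | Power |
|---|---|---|
| Unstratified rank-sum on change | 3.4/3.0/1.7% | 59/66/80% |
| Van Elteren on change | 4.8/4.9/4.8% | 65/74/88% |
| Rank ANCOVA, baseline and domain | 5.2/4.9/5.3% | 74/81/91% |
| ANCOVA, log scale | 4.8/5.2/4.8% | 77/84/95% |

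With no shift, stratifying gains nothing: unstratified power is 59/73/89% and van Elteren 58/71/88%.

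**The case against.** A reader might infer that the SAP switches the pooled analysis of non-normal data to an unstratified rank-sum test, so that baseline and domain are both dropped and the pooled test is over-conservative. The documents do not support this. The rank-sum sentence is confined to by-domain analyses, where there is no domain term to lose and type I error is nominal. The pooled text names no rank test, and van Elteren or rank ANCOVA would fit its wording. The mock-up tables that might settle the matter are separate documents (SAP 3.6). By domain too, the text offers a choice and not a switch.

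Other objections stand in part:

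- **Log-transformation is already permitted.** It keeps ANCOVA with its adjusters, and with log-normal data it beats rank ANCOVA. It should stay. It suits right-skewed data, however. SpO2/FiO2 starts near its ceiling, since entry requires SpO2 of at least 94% on room air, so its long tail would point downwards, which a log does not cure.
- **Power loss depends on the comparator.** By domain, the rank-sum test on change beats raw-scale ANCOVA on skewed data (31/40/59% against 28/31/44%). The loss is against rank or log-scale ANCOVA.
- **The ANCOVA benchmark is not guaranteed.** SAP 3.2.2 says that "those non-statistically significant factors except treatment will be removed from the model (alpha=0.1 for interaction, 0.05 for others"), so baseline or domain may leave the model. The pooled categorical tests may also be unstratified, because Fisher's exact test is offered beside the stratified one.
- **The stakes are small.** The primary endpoint is binary, the study is exploratory and not sized on power, and no stated decision rule depends on these p-values.

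**Conclusion.** The point holds in a limited form. The by-domain rank option omits a baseline covariate that the trial collects and that its ANCOVA uses. Under the stated assumptions this costs about 7 to 18 points of power at a correlation of 0.3 to 0.5, and 1 to 4 points at 0.7 if change is what is ranked.

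For pooled comparisons the finding is a gap in specification, not a wrong test. The drop in type I error to about 1 to 3% is conditional twice over: on an unstratified rank-sum being chosen, and on the domains differing by about 1 SD. If they do not differ, the test is close to nominal.

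The pooled point concerns SpO2/FiO2, the biomarkers, the cytokines and continuous safety measures. Viral load and Ct values are analysed in the SARS-CoV-2 domain only, so the domain argument does not reach them. The baseline argument does, if they are tested by ranks. This is a cheap improvement to consider. It does not threaten the primary result.

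**What to change.** In SAP 3.2.2 and 3.4.3:

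1. Replace the rank-sum option for post-baseline continuous data with a rank analysis of covariance: rank the post-baseline and baseline values, then fit treatment and baseline rank, plus domain when pooled. At minimum, use the van Elteren test stratified by domain for any pooled rank comparison.
2. Keep log-scale ANCOVA as the permitted alternative, and state before unblinding when the raw scale, log scale or ranks will be used.
3. Keep the plain rank-sum test for baseline data within a domain.

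The cost is one or two sentences and a few lines of standard SAS (PROC RANK with PROC GLM, or PROC FREQ with modified ridit scores for van Elteren). No new data are needed. There are two downsides. A rank ANCOVA p-value needs a separate effect estimate, as the rank-sum p-value does. There is also little or no gain over ranking the change when the baseline correlation is high.

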7.3. General Consideration

Statistical analyses will be performed using SAS® for Windows, version 9.4 or later. All available data will be displayed via subject data listings, and summarized for each evaluation time point as appropriate by study domain (including domain-pooled) and study arm. The categorical data will be summarized with the number of subjects and percentage. Continuous data will be summarized by descriptive statistics (i.e., number of subjects, mean, standard deviation, minimum, maximum, and median). For by visit (by Day) analyses, the acceptable window for each visit will be defined in the Statistical Analysis Plan (SAP).

In general, categorical data will be analyzed by using Logistic regression (on efficacy data), Fisher's exact test or Cochran-Mantel-Haenszel test stratified by domain for comparing overall treatment group difference (treatment odds ratio for Logistic regression). For by-domain subgroup analysis on efficacy data, categorical data will be tested by using Fisher's exact test or Chi-square test.

Continuous data will be analyzed by using analysis of variance (ANOVA) on baseline data, and by using analysis of covariance (ANCOVA) on change data for comparing overall treatment group difference. Non-parametric method shall be adapted or log-transformation may be needed for non-normally distributed data. For by-domain subgroup analysis on efficacy data, continuous data will be tested by using two-sample t test or Wilcoxon Rank-sum test.

For the ANOVA, ANCOVA model and Logistic regression, factors of treatment, domain (as appropriate), site and baseline value (for post-baseline data) and other baseline factors (for post-baseline efficacy data, to be defined in the SAP, as appropriate) will be included in the model if significant, those non-statistically significant factors except treatment will be removed from the model (alpha=0.1 for interaction, 0.05 for others). The Logistic regression result will be presented with treatment odds ratio and its 95% confidence interval (CI).

All statistical tests will be two-sided and evaluated at the 0.05 level of significance. All confidence intervals, if provided, will be the 95% CI.

The most recent value before first dose administration will be defined as the baseline value; therefore, the baseline value will be the outcome of the closest evaluation performed before or equal to the first dosing date.

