#### **3.4.2 HANDLING OF DOMAIN IN STATISTICAL ANALYSIS**

For subjects with positive FilmArray results for both SARS-CoV-2 and Influenza Virus, the domain used for statistical analyses, including but not limited to subgroup analysis and ANOVA/ANCOVA modeling, will be conducted based on their randomized domain group.

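### SAP 3.2.2 and 3.3.1 conflict on whether domain and baseline value stay in the ANOVA/ANCOVA whatever their p-values

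*SAP*

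**What the plan says.** SAP 3.2.2 takes over the factor-selection rule of Protocol 7.3. It lists treatment, domain, site, baseline value and other baseline factors, ending "baseline value (for post-baseline data) and other baseline factors will be included in the model if significant", and continues: "those non-statistically significant factors except treatment will be removed from the model (alpha=0.1 for interaction, 0.05 for others". No interaction is named.

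SAP 3.3.1 explains that most sites enrolled few subjects after early termination, takes site out of the models, and states: "only treatment, domain (as appropriate), and baseline value (for post-baseline data) are the factors in the ANOVA and ANCOVA model". It neither repeats nor withdraws the significance condition.

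Three other places bear on the question.

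- SAP 2.2 describes "stratified randomization with study domains and study sites strata", so domain is a randomization stratum.
- SAP 3.4.2 covers subjects positive for both viruses. Their domain for analysis, "including but not limited to subgroup analysis and ANOVA/ANCOVA modeling, will be conducted based on their randomized domain group".
- Protocol 7.3 says "For by-domain subgroup analysis on efficacy data, continuous data will be tested by using two-sample t test or Wilcoxon Rank-sum test". SAP 3.4.3 changes this for data after treatment: "post-treatment continuous data will be tested by using ANCOVA or Wilcoxon Rank-sum test".

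SAP 3.4.1 to 3.4.5 list the changes from the protocol analyses. None of them mentions the selection rule or the removal of site.

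**The concern.** Two programmers working from this SAP could build different models. One would fit the 3.3.1 factors every time. The other would start from those factors and delete domain or baseline value wherever p exceeds 0.05. In the second case, whether a result is adjusted for baseline, or for a randomization stratum, would vary by endpoint, visit, domain and analysis population, and effects would not be comparable across tables. Within one domain, baseline value is the only covariate left. Deleting it turns the ANCOVA of 3.4.3 back into the t test that 3.4.3 replaced.

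The analyses at stake are the parametric ones of continuous data: change in SpO2/FiO2, viral load, Ct value, inflammatory markers, cytokines, and continuous laboratory, vital-sign and ECG values. The primary endpoint, all-cause events, X-ray, NIAID status and RT-PCR negativity use tests for categorical data, and fever uses a log-rank test. None of these depends on the rule, and neither does any endpoint moved to a rank test.

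**Working it through.** **Inputs from the documents.** 44 subjects were randomized (SAP 3.4.1), and the ITT population is those also dosed (SAP 3.1), so N is at most 44. Allocation is 1:1 (SAP 2.2). Tests are two-sided at 0.05, and the removal threshold is 0.05 (SAP 3.2.2).

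**Assumed, because the documents give no values.** Baseline/post-baseline correlation ρ of 0.2 to 0.8; domain effect 0 to 0.5 SD; domain split 22:22 or 12:32; single-domain n of 12, 22 or 32; normal data. The plan states no figure on this point. Its enrolment figure reproduces (120/4 = 30 per arm; 30/0.9 = 33.3, rounded up to 34; 4 × 34 = 136) but does not enter here.

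**Step 1: the two readings.**

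| | 3.3.1 is a fixed model | 3.3.1 is a candidate list |
|---|---|---|
| Pooled change | treatment + domain + baseline value | treatment + whichever of the two has p ≤ 0.05 |
| Single-domain change | treatment + baseline value | ANCOVA or t test, depending on the baseline p-value |
| For it | no significance condition in 3.3.1; keeps 3.4.2 and 3.4.3 effective | 3.2.2 stands unamended; 3.4 records no withdrawal |
| Left unresolved | 3.2.2 contradicts it; the 3.4 entry is missing | partly undoes 3.4.2 and 3.4.3 |

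Either way the text needs reconciling.

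**Step 2: how often baseline value would be dropped.** With unit variances, post = ρ × baseline + √(1−ρ²) × noise. The change then has slope −(1−ρ) on baseline and residual SD √(1−ρ²). The expected size of the t statistic is roughly √(n(1−ρ)/(1+ρ)).

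- n=44, ρ=0.5: √(44×0.5/1.5) = 3.83; simulated drop rate 6–7%
- n=44, ρ=0.8: √(44×0.2/1.8) = 2.21; 44–46%
- n=22, ρ=0.8: √(22×0.2/1.8) = 1.56; 71%
- n=12, ρ=0.8: √(12×0.2/1.8) = 1.15; 84%
- n=32, ρ=0.2: √(32×0.8/1.2) = 4.62; 2%

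In the pooled model, domain would be dropped in about 95% of trials if it has no effect. If its effect is 0.5 SD, it would be dropped in 25–55% at ρ = 0.8 to 0.5.

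**Step 3: why the cost is limited.** Large-sample variance without baseline relative to variance with it is 2(1−ρ)/(1−ρ²) = 2/(1+ρ). This is 1.67 at ρ=0.2, 1.33 at 0.5 and 1.11 at 0.8. Baseline is dropped often mainly where dropping it costs little. The exception is a small single domain with low correlation.

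**Step 4: simulation.** No treatment effect; backward elimination at 0.05, least significant factor first, against the fixed 3.3.1 model. There were 100,000 trials per cell (standard error of type I error √(0.05×0.95/100,000) = 0.07 points), except 60,000 for the n=32, ρ=0.2 cell.

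| Setting | Baseline dropped | Variance of estimate | Type I error | Models disagree at p<0.05 |
|---|---|---|---|---|
| Pooled N=44, ρ 0.5–0.8 | 6–46% | +1.4 to +3.8% | 5.0–5.6% | 0.4–1.1% |
| Pooled N=44, ρ 0.2 | 0.3–0.4% | at most +0.2% | 4.9–5.2% | not tabulated |
| One domain, n=22, ρ 0.2–0.8 | 10–71% | +5 to +8% | 5.5–5.9% | 0.5–1.6% |
| One domain, n=12–32, ρ 0.5–0.8 | 16–84% | +1 to +13% | 5.3–6.4% | 0.5–2.3% |
| Mildest single-domain cell: n=32, ρ 0.2 | 2% | +0.9% | 5.1% | 0.1% |
| Worst cell: n=12, ρ 0.2 | not tabulated | +18% | 6.5% | not tabulated |

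The fixed model gave type I error of 4.9–5.1% pooled and 4.8–5.1% in one domain. With a 0.6 SD treatment effect and a 0.5 SD domain effect at N=44 (10,000 trials), power was 60.1%, 76.1% and 88.9% fixed, against 59.8%, 75.4% and 88.4% with removal, at ρ = 0.5, 0.7 and 0.8. Coverage of the 95% interval under removal was 94.3–95.1% over N = 40 and 44 and ρ of 0.3 to 0.9. Interactions were not simulated, because none is named.

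**The case against.** The strongest reply is that 3.3.1 is the later and more specific section, is headed as the covariate section, and states flatly what the factors are. If it overrides 3.2.2 on site and on other baseline factors, it may equally override the significance condition in the same sentence. A reading that would undo 3.4.2 and 3.4.3 is also the less natural one. On this view the 3.2.2 sentence is leftover protocol text. This largely stands: a reader might infer that domain and baseline value will in fact be selected by p-value, and the documents do not establish that. What remains is that 3.2.2 was not amended and 3.4 is silent.

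A second reply is that the harm is slight and confined to exploratory analyses in a trial not sized for power. That also stands. A reader might infer that the rule endangers the trial's main conclusion, or that it was devised after seeing data. Neither is supported. The primary endpoint uses Fisher's exact or Cochran-Mantel-Haenszel tests. The rule came in with protocol version 2.0, dated 5 February 2024, before the first enrolment on 20 March 2024.

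Third, the simulation assumes normal data. Cytokines, inflammatory markers and viral load may be skewed, and the SpO2 entry criterion narrows the baseline SpO2/FiO2 range. Endpoints moved to rank tests escape the issue, so fewer analyses may be affected than the list suggests.

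**Conclusion.** The two sections conflict, and the SAP does not say which governs; confidence in that is high. That covariates would actually be dropped is a possible consequence, held with medium confidence. If it happened, the pooled effect would be minor. The larger effect would be in single-domain analyses: over n = 12 to 32 and correlation 0.2 to 0.8, baseline value is dropped in 2–84% of analyses, variance rises by about 1–18%, and type I error is about 5.1–6.5%. All these figures rest on assumed correlations, domain sizes and normality. No confirmatory conclusion changes. The point is worth correcting, at low to moderate priority, because the model behind each continuous result should be known in advance and be the same across tables.

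**What to change.** - **SAP 3.2.2:** replace the factor sentence with: *The factors in the ANOVA and ANCOVA models are those in section 3.3.1; no factor is removed on significance.* This also removes site, other baseline factors and the 0.1 threshold for an unnamed interaction.
- **SAP 3.3.1:** replace the qualifier on domain with the models themselves. Pooled change: treatment + domain + baseline value. Single-domain change, including viral load and Ct: treatment + baseline value. Pooled baseline ANOVA: treatment + domain.
- **SAP 3.4:** add an entry that the Protocol 7.3 selection rule and the site factor are dropped, citing the sparse-site reason already given in 3.3.1.

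The cost is wording in two sections and one new entry. No further data are needed, and fixed models take less programming than factor selection. If treatment codes have already been opened, the report should state which model was run for each table.
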